3. INTERIM ANALYSIS AND DATA MONITORING COMMITTEE REVIEW

An IDMC will be established to monitor data on an ongoing basis to ensure the continuing safety of the subjects enrolled in this study. The committee will meet every 6 months to review safety data. After the reviews, the IDMC will make recommendations regarding the continuation of the study.

The IDMC will review CIOMS (Council for International Organizations of Medical Sciences) reports and summaries of AEs including AEs by preferred term, serious adverse events (SAE), and discontinuations due to AEs. Details about the review to be performed and the roles and responsibilities of the IDMC are presented in a separate IDMC charter.

Interim analyses will be performed on as needed basis (e.g. request from health authorities). Details of statistical output required for the interim analyses will be defined in the Data Presentation Specifications.

Sensitivity/exploratory analyses may be conducted for efficacy and safety variables of interest to evaluate the impact missed doses and/or remote visits which occurred due to COVID-19.

4. SUBJECT INFORMATION

4.1. Demographics and Baseline Characteristics

Demographic and baseline characteristics (Table 2) and psychiatric history at baseline (Table 3) will be summarized for the All Enrolled analysis set (described in Section 2.4.1). Continuous variables will be summarized using descriptive statistics (N, mean, standard deviation [SD]),

median, minimum, and maximum). Categorical variables will be summarized using a frequency distribution with the number and percentage of subjects in each category. Baseline values (described in Section 2.2) will be used for these summaries.

Table 2: Demographic Variables and Baseline Characteristics

Continuous Variables:

- Age (years)
- Baseline weight (kg)
- Baseline height (cm)
- Baseline BMI (kg/m²) calculated as Weight (kg)/[Height (m)]²

Categorical Variables:

- Age in years (18 - 44, 45 - 64, 65 – 74, ≥ 75)
- Sex (male, female)
- Race^a (White, Black or African American, Asian, American Indian or Alaskan native, Native Hawaiian or other Pacific islander, other)
- Ethnicity (Hispanic or Latino, not Hispanic or Latino)
- Baseline BMI (underweight: < 18.5 kg/m², normal: 18.5 to < 25 kg/m², overweight: 25 kg/m² to < 30 kg/m², obese: 30 to < 40 kg/m², morbidly obese: ≥ 40 kg/m²)
- Employment Status
- Hypertension Status
- Country
- Region

^a If multiple race categories are indicated, then Race is recorded as “Multiple”.

Table 3: Psychiatric History at Baseline Variables

Continuous Variables:

- Baseline MADRS total score
- Baseline PHQ-9 total score
- Baseline CGI-S score
- Age (years) when diagnosed with major depressive disorder (MDD)
- Duration of current episode

Categorical Variables:

- Baseline CGI-S score
- Baseline C-SSRS category (no event, suicidal ideation, suicidal behavior)
- Family history of
 - Depression
 - Anxiety Disorder
 - Bipolar Disorder
 - Schizophrenia
 - Alcohol Abuse
 - Substance Abuse

Note: The psychiatric history is derived from the first study subjects participated in. For example, if a subject first participated in ESKETINTRD3001, then went on to ESKETINTRD3003 and continued to participate in 54195413TRD3008, the psychiatric history is obtained from the ESKETINTRD3001 database and will be copied to the 54195413TRD3008 database.

4.2. Disposition Information

The number of subjects who enrolled from studies ESKETINTRD3001, ESKETINTRD3002, ESKETINTRD3003, ESKETINTRD3004, ESKETINTRD3005, or ESKETINTRD3006 (US sites only) will be provided.

The following disposition summaries will be provided for IND and OP/MA phases separately. These summaries will be provided for each of the Full analysis sets described in Section 2.4.2.

- The number of subjects who entered a specific treatment phase
- The number of subjects who discontinued a specific treatment phase prematurely and their reasons for discontinuation
- The number of subjects who are ongoing in each phase at the time the sponsor terminated the study.

The number of subjects who terminated the trial and the reasons for ending study participation throughout the study will also be summarized. This will be summarized for All Enrolled analysis set described in Section 2.4.1.

4.3. Extent of Exposure

Extent of exposure in terms of total duration of exposure and number of dosing sessions of intranasal study medication will be summarized by phase for the Full analysis sets and across both phases for the All Enrolled analysis set described in Section 2.4.2.

- The total duration of exposure for the intranasal study drug for each phase is defined as the time between the first and the last dose of study medication in that specific phase (last day of study medication - first day of study medication + 1). If a subject only receives a partial dose it is considered as a day of dosing.

Descriptive statistics (N, mean, SD, median, minimum and maximum) and frequency distribution of total duration of exposure of intranasal study drug will be presented. A frequency distribution of the total number of dosing sessions of intranasal study medication will be presented.

Starting at Week 4, during the optimization/maintenance phase, the number and percentage of subjects at each dosing frequency (weekly, every other week and every 4 weeks) and the number of subjects who changed their frequency will be summarized every 4 weeks.

- Modal dose for a subject is defined as the most frequently taken dose by a subject. Mean dose of a subject is calculated as the sum of doses during the phase divided by the total number of days exposed in the phase. The final dose is the last non-zero dose received during the phase. The calculation of mean, modal and final dose will exclude days off study drug.

Descriptive statistics (N, mean, SD, median, minimum and maximum) of modal dose, mean and final dose of intranasal study drug will be presented by phase. A frequency distribution of dose level (28, 56 and 84 mg) will be presented at each dosing session. In addition, at end of each phase the number and percentage of subjects at each dose (28, 56 and 84 mg) of intranasal study medication will be provided.

4.4. Protocol Deviations

Deviations that occurred during the study will be tabulated for the All Enrolled analysis set. Major deviations will be tabulated for the following categories: subject not withdrawn as per protocol, selection criteria not met, excluded concomitant treatment, treatment deviation, non-compliance, regulatory requirement. More categories may be included depending on the nature of the protocol deviation.

4.5. Concomitant Medications

The number and percent of subjects who receive concomitant therapies will be summarized by phase using the generic term of the medication for the Full (IND, OP/MA) analysis sets described in Section 2.4.2.

5. EFFICACY

5.1. Analysis Specifications

5.1.1. Data Handling Rules

For the efficacy scales MADRS, CGI-S, PHQ-9, and SDS both observed case and last observation carried forward (LOCF) values will be determined for the induction, optimization/maintenance phases. For analysis performed by phase, LOCF will be performed within the respective phase. For analysis performed for entire treatment phase, induction data will be carried forward to optimization/maintenance. Besides the observed cases and the end point assessment, the LOCF values will be created for intermediate postbaseline time points as well. These imputed time points will be labeled as ‘Day X LOCF’ or ‘Week X LOCF’

5.1.2. Imputation Methods for Missing Items

Imputation of the MADRS total score is described in Section 5.2.1.1. For all other scales where multiple items are summed to create a total, if any item of the scale is missing at a visit, the total score for that scale at that visit will be considered missing.

5.2. Efficacy Endpoints

Efficacy analyses during the induction phase and the optimization/maintenance phase will be provided for the Full analysis sets defined in Section 2.4.2.

5.2.1. Montgomery-Asberg Depression Rating Scale (MADRS)

5.2.1.1. Definition

The MADRS is a clinician-rated scale designed to measure depression severity and to detect changes due to antidepressant treatment⁵. The scale consists of 10 items, each of which is scored from 0 (item is not present or is normal) to 6 (severe or continuous presence of the symptoms), for a total possible score of 60. Higher scores represent a more severe condition. The MADRS evaluates apparent sadness, reported sadness, inner tension, sleep, appetite, concentration, lassitude, interest level, pessimistic thoughts, and suicidal thoughts. The test exhibits high inter-rater reliability.

If 2 or more items are missing, no imputation will be performed and the total score will be left missing. Otherwise, the total score will be calculated as sum of the non-missing items multiplied by the ratio of the maximum number of items (i.e., 10) to the number of non-missing items.

A subject is defined a responder at a given time point if the percent improvement in MADRS total score is $\geq 50\%$.

A subject is defined as a remitter at a given time point if the MADRS total score of ≤ 12 at that time point.

5.2.1.2. Analysis Methods

Descriptive statistics of the total score and change from baseline (of the respective phase) will be provided for each visit during both IND and OP/MA phases. Graphical presentations will be provided. In addition, the proportion of subjects who responded and remitted based on the MADRS total score will be provided over time for each phase. Summaries of both observed and LOCF data will be presented.

For subjects who had relapsed in ESKETINTRD3003 and participated in a second induction treatment phase, the proportion of responders and remitters using the MADRS total score at the end of the second induction phase will be provided.

5.2.2. Clinical Global Impression – Severity (CGI-S)

5.2.2.1. Definition

The CGI-S provides an overall clinician-determined summary measure of the severity of the subject's illness that takes into account all available information, including knowledge of the subject's history, psychosocial circumstances, symptoms, behavior, and the impact of the symptoms on the subject's ability to function³. The CGI-S evaluates the severity of psychopathology on a scale of 0 to 7. Considering total clinical experience, a subject is assessed on severity of mental illness at the time of rating according to: 0 = not assessed; 1 = normal (not at all ill); 2 = borderline mentally ill; 3 = mildly ill; 4 = moderately ill; 5 = markedly ill; 6 = severely ill; 7 = among the most extremely ill patients. The CGI-S permits a global evaluation of the subject's condition at a given time.

5.2.2.2. Analysis Methods

Descriptive statistics of the medians and median change from baseline (of the respective phase) will be provided for each visit during both IND and OP/MA phases. In addition, a frequency distribution will be provided for each visit for both phases. Summaries of both observed and LOCF data will be presented.

5.2.3. Patient Health Questionnaire – 9 item (PHQ-9)

5.2.3.1. Definition

The PHQ-9 is a 9-item, self-report scale assessing depressive symptoms⁸. Each item is rated on a 4-point scale (0 = Not at all, 1 = Several Days, 2 = More than half the days, and 3 = Nearly every day), with a total score range of 0-27. A higher score indicates greater severity of depression. The recall period is 2 weeks. The scale scores each of the nine symptom domains of the Diagnostic and Statistical Manual of Mental Disorders (DSM) Major Depressive Disorder criteria and it has been used both as a screening tool and a measure of response to treatment for depression. The severity of the PHQ-9 is categorized as follows: None-minimal (0 - 4), Mild (5 - 9), Moderate (10 - 14), Moderately Severe (15 - 19) and Severe (20 - 27). A subject is defined as a responder at a given time point if the percent improvement from baseline in PHQ-9 total score is $\geq 50\%$. A subject is defined as a remitter at a given time point if the PHQ-9 total score is < 5 at that time point.

5.2.3.2. Analysis Methods

Descriptive statistics of the total score and change from baseline (of the respective phase) will be provided for each visit during both IND and OP/MA phases. The frequency of severity categories will be summarized over time during each phase. Graphical presentations will be provided. In addition, the proportion of subjects who achieve response and remission based on the PHQ-9 total score will be summarized for each visit during both phases. Summaries of both observed and LOCF data will be presented.

For subjects who had relapsed in ESKETINTRD3003 and participated in a second induction treatment phase, the proportion of subjects who achieve response and remission at the end of the second induction phase will be provided.

5.2.4. Sheehan Disability Scale (SDS)

5.2.4.1. Definition

The SDS is a subject-reported outcome measure and is a 5-item questionnaire which has been widely used and accepted for assessment of functional impairment and associated disability. The first three items assess disruption of (1) work/school, (2) social life, and (3) family life/home responsibilities using a 0-10 rating scale. The score for the first three items are summed to create a total score of 0-30 where a higher score indicates greater impairment. It also has one item on days lost from school or work and one item on days when underproductive. The recall period for this study is 7 days. Scores ≤ 4 for each item and ≤ 12 for the total score are considered response. Scores ≤ 2 for each item and ≤ 6 for the total score are considered remission. If any of the first

three items are missing, the total score will be set to missing as well as response and remission status.

5.2.4.2. Analysis Methods

Descriptive statistics of the total score and change from baseline (of the respective phase) will be provided for each visit during both IND and OP/MA phases. Graphical presentations will be provided. Summaries of both observed and LOCF data will be presented. The total score as well as the individual item scores will be summarized. In addition, the proportion of subjects who achieve response and remission will be summarized at each time point.

5.2.5. EuroQol Group; 5 Dimension; 5 level (EQ-5D-5L)

5.2.5.1. Definition

The EQ-5D-5L^{1,2} is a standardized 2-part instrument for use as a measure of health outcome, primarily designed for self-completion by respondents. It essentially consists of the EQ-5D-5L descriptive system and the EQ visual analogue scale (EQ VAS). The EQ-5D-5L descriptive system comprises the following 5 dimensions: mobility, self-care, usual activities, pain/discomfort and anxiety/depression. Each of the 5 dimensions is divided into 5 levels of perceived problems (Level 1 indicating no problem, Level 2 indicating slight problems, Level 3 indicating moderate problems, Level 4 indicating severe problems, and Level 5 indicating extreme problems).

The subject selects an answer for each of the 5 dimensions considering the response that best matches his or her health “today.” The descriptive system can be represented as a health state. The EQ VAS self-rating records the respondent’s own assessment of his or her overall health status at the time of completion, on a scale of 0 (the worst health you can imagine) to 100 (the best health you can imagine).

The time taken to complete the questionnaire varies with age, health status, and setting but is likely to be around 1 minute.

Individual scores from the 5 dimensions will be used to obtain a weighted health status index as shown below:

- i) Scores from each dimension will be combined to obtain a 5L profile score or health state: e.g., a score of 1 for each dimension will give a 5L profile score of 11111. Dimension scores will be combined in the following order: Mobility, Self-Care, Usual Activities, Pain/Discomfort, Anxiety/Depression
- ii) The value set of the Health Status Index for various values of 5L profile scores is published for Canada in the following website:
<https://www.ncbi.nlm.nih.gov/pubmed/26492214>
- iii) The Canadian value set will be used to get the HSI values for all the countries participating in the study

In addition, a sum score will be derived as follows: The scores of the five dimensions (values 1-5) will be added (sums between 5 and 25). From this score, subtract 5 (range 0-20) and multiply by 5 (range 0-100).

5.2.5.2. Analysis Methods

Descriptive statistics of actual values and changes from baseline for the weighted EQ-5D health status index, the EQ VAS, and the sum score will be summarized for each visit for both IND and OP/MA phases. In addition, a frequency distribution will be provided for each individual dimension at each visit for both phases. Summaries of observed data will be presented.

5.2.6. Treatment Satisfaction Questionnaire for Medication (TSQM-9)

5.2.6.1. Definition

The TSQM-9 is a 9-item generic patient reported outcome instrument to assess patients' satisfaction with medication. It is derived from the longer TSQM Version 1.4 and covers domains of effectiveness (item 1-Satisfied, Ability to Treat; item 2-Satisfied, Relieves Symptoms; item 3-Satisfied, Time It Takes to Work), convenience (item 4-Easy/Difficult to Use the Med; item 5-Easy/Difficult to Plan the Use; item 6 -Convenient, Take Med as Instructed) and global satisfaction (item 7-Confident Taking This Med Is Good; item 8-Certain, Good Things Outweigh Bad; item 9-How Satisfied, Overall). The instrument is scored by domain with a transformed scores ranging from 0-100 where a lower score indicates lower satisfaction. The recall period is "the last 2-3 weeks".

Scoring algorithm

Effectiveness:

$[(\text{Item 1} + \text{Item 2} + \text{Item 3}) - 3] \text{ divided by } 18) \times 100$

If one item is missing: $[\text{Sum of two completed items} - 2] \text{ divided by } (12) \times 100$

Convenience:

$[(\text{Sum of Item 4 to Item 6}) - 3] \text{ divided by } 18) \times 100$

If one item is missing: $[\text{Sum of two completed items} - 2] \text{ divided by } (12) \times 100$

Overall satisfaction:

$[(\text{Sum}(\text{Item 7 to Item 9}) - 3) \text{ divided by } 14) * 100$

If either Item 7 or 8 is missing

$[(\text{Sum}(\text{the two completed items})) - 2] \text{ divided by } 10) * 100$

If Item 9 is missing

$[(\text{Sum}(\text{Item 7 and Item 8})) - 2] \text{ divided by } 8) * 100$

5.2.6.2. Analysis Methods

Descriptive statistics of the transformed score and change from baseline (of the respective phase) will be provided for each domain by visit during both IND and OP/MA phases. Summaries of observed data will be presented.

5.2.7. Quality of Life in Depression Scale (QLDS)

5.2.7.1. Definition

The QLDS is a disease specific PRO designed to assess health related quality of life in patients with Major Depressive Disorder. The instrument has a recall period of “at the moment”, contains 34-items with “yes” / “no” response options and takes approximately 5-10 minutes to complete. The score range is from 0 (good quality of life) to 34 (very poor quality of life).

5.2.7.2. Analysis Methods

Descriptive statistics of the total score and change from baseline (of the respective phase) will be provided for each visit during both IND and OP/MA phases. Summaries of observed data will be presented.

6. SAFETY

Safety data for the induction and optimization/maintenance phases will be presented separately for each phase. Summaries for each phase will be based on the Full analysis sets described in Section 2.4.2. In addition, adverse event and cognition data will be summarized for the entire treatment period combining the induction and optimization/maintenance phases. Summaries for the entire treatment period will be based on the All Enrolled analysis set described in Section 2.4.1.

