Medical resource utilization data, associated with medical encounters, will be collected using the Healthcare Resource Use Questionnaire (HRUQ). The HRUQ includes information regarding utilization of healthcare services (including the timing and type of services), enabling changes in level and quantity of services to be considered as a variable in economic models.

STATISTICAL METHODS

Analysis Sets

The following analysis sets will be used to summarize efficacy and safety data.

- Full Analysis Set for Induction phase: will be defined as all subjects who receive at least one dose of esketamine nasal spray during this phase.
- Full Analysis Set for Optimization/Maintenance phase: will be defined as all subjects who receive at least one dose of esketamine nasal spray during this phase.

Sample Size Determination

No formal sample size calculation was performed as only subjects who have participated in the other Phase 3 studies may participate in this study.

Safety Analysis

Safety data for the induction phase and the optimization/maintenance phase will be analyzed separately for each phase as well as for the entire treatment period (induction and optimization/maintenance phase).

Computerized cognitive test battery and HVLT-R scores and their changes from baseline will be summarized at each scheduled time point using descriptive statistics.

Adverse events will be coded using the Medical Dictionary for Regulatory Activities (MedDRA). For each adverse event, the percentage of subjects who experience at least 1 occurrence of the given event will be summarized. Subjects who die, who discontinue treatment due to an adverse event, or who experience a severe or a serious adverse event will be summarized separately.

Treatment emergent AEs of special interest will be examined separately grouped in the following categories: drug abuse, dependence and withdrawal, increased blood pressure, increased heart rate, transient dizziness/vertigo, impaired cognition, cystitis, anxiety, events potentially related to suicidality, hepatic adverse events, events related to renal disorders, and symptoms of dissociation persisting beyond the typical ≤ 2 hour post esketamine administration, as well as delirium, psychosis or mania.

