11.3. Safety Analyses

Safety data for the induction phase and the optimization/maintenance phase will be presented separately for each phase as well as for the entire treatment period (induction and optimization/maintenance phase). The baseline for safety assessments will be defined in the Statistical Analysis Plan.

Cognitive Function

Computerized cognitive test battery and HVLT-R: Descriptive statistics of each of the cognitive domain scores and changes from baseline will be provided at each scheduled time point.

Adverse Events

The verbatim terms used in the CRF by investigators to identify adverse events will be coded using the Medical Dictionary for Regulatory Activities (MedDRA). Treatment-emergent adverse events are adverse events with onset during the treatment phase or that are a consequence of a pre-existing condition that has worsened since baseline. All reported adverse events with onset during the treatment phase (ie, TEAEs, and adverse events that have worsened since baseline) will be included in the analysis. For each adverse event, the percentage of subjects who experience at least 1 occurrence of the given event will be summarized.

Treatment emergent AEs of special interest will be examined separately grouped in the following categories: drug abuse, dependence and withdrawal, increased blood pressure, increased heart rate, transient dizziness/vertigo, impaired cognition, cystitis, anxiety, events potentially related to suicidality, hepatic adverse events, events related to renal disorders, and symptoms of dissociation persisting beyond the typical ≤ 2 hour post esketamine administration, as well as delirium, psychosis or mania.

Summaries, listings, datasets, or subject narratives may be provided, as appropriate, for those subjects who die, who discontinue treatment due to an adverse event, or who experience a severe or a serious adverse event.

Vital Signs

Descriptive statistics of body weight, temperature, pulse/heart rate, respiratory rate, pulse oximetry and supine blood pressure (systolic and diastolic) values and changes from baseline will be provided at each scheduled time point. Any treatment-emergent abnormalities will be listed.

Clinical Laboratory Tests

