6.3. Vital Signs, Weight, and BMI

Descriptive statistics for values and changes from Baseline values (described in Section 2.2) at each scheduled time-point during the induction and optimization/maintenance phases will be presented for temperature, systolic blood pressure, diastolic blood pressure, pulse rate, respiratory rate, oxygen saturation, weight, and BMI. Baseline will be used for change summaries and to determine abnormal values during all treatment phases (IND and OP/MA). Graphical presentations will be provided.

In addition, descriptive statistics of pulse rate and blood pressure (systolic and diastolic) values and changes and percent changes from predose will be provided for each intranasal dosing day.

The proportion of subjects who have a treatment-emergent abnormality, as defined in Table 4 below, during each treatment phase will be presented. A listing of subjects meeting any of the following criteria during each treatment phase will also be provided.

Table 4: Treatment-Emergent Abnormality Categories for Vital Signs

Vital Parameter	Post-baseline value outside of normal limit if:	
	Abnormally low	Abnormally high
Pulse (bpm)	A decrease from Baseline of ≥ 15 to a value ≤ 50	An increase from Baseline of ≥ 15 to a value ≥ 100
Systolic BP (mmHg)	A decrease from Baseline of ≥ 20 to a value ≤ 90	An increase from Baseline of ≥ 20 to a value ≥ 180
Diastolic BP (mmHg)	A decrease from Baseline of ≥ 15 to a value ≤ 50	An increase from Baseline of ≥ 15 to a value ≥ 105

BP = blood pressure; Baseline is defined in Section 2.2.

The proportion of subjects who experienced treatment-emergent acute hypertension (systolic BP ≥ 180 or diastolic BP ≥ 110) at any time during each treatment phase will be summarized by hypertension status.

Mean (+/-SE) values for systolic BP, diastolic BP and heart rate will be summarized by hypertension status and presented graphically for each treatment phase. In addition, for subjects with hypertension who receive antihypertensive medication, the same tables and graphs will be summarized by medication type (beta-blockers, all other agents).

A listing of subjects with oxygen saturation less than 93% will be provided.

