6.6. Other Safety Parameters

6.6.1. Columbia-Suicide Severity Rating Scale (C-SSRS)

The C-SSRS⁷ is a low-burden measure of the spectrum of suicidal ideation and behavior that was developed in the National Institute of Mental Health Treatment of Adolescent Suicide Attempters Study to assess severity and track suicidal events through any treatment. It is a semi structured clinician-administered questionnaire designed to solicit the occurrence, severity, and frequency of suicide-related ideation and behaviors during the assessment period. Using the C-SSRS, potentially suicide-related events will be categorized using the following scores:

Suicidal Ideation (1-5)

- 1: Wish to be Dead
- 2: Non-specific Active Suicidal Thoughts
- 3: Active Suicidal Ideation with Any Methods (Not Plan) without Intent to Act
- 4: Active Suicidal Ideation with Some Intent to Act, without Specific Plan
- 5: Active Suicidal Ideation with Specific Plan and Intent

Suicidal Behavior (6-10)

- 6: Preparatory Acts or Behavior
- 7: Aborted Attempt
- 8: Interrupted Attempt
- 9: Actual Attempt (non-fatal)
- 10: Completed Suicide

If no events qualify for a score of 1 to 10, a score of 0 will be assigned (0 = “no event that can be assessed on the basis of C-SSRS”). Higher scores indicate greater severity.

The summaries of the C-SSRS outcomes will be based on the Full analysis set for subjects who have at least 1 post-baseline C-SSRS measurement and a pre-treatment C-SSRS assessment.

A frequency distribution at each scheduled time point will be provided. Shifts from the Baseline value (described in Section 2.2) to the most severe/maximum score during each phase will be summarized.

The maximum score assigned for each subject will also be summarized into one of three broad categories: No suicidal ideation or behavior (0), Suicidal ideation (1 - 5), Suicidal behavior (6 - 10). Shifts from the Baseline value (described in Section 2.2) to the maximum category during each phase will be summarized.

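### The protocol promises safety results for the entire treatment period, but the SAP plans them only for adverse events and cognition; whole-period incidence of measured acute hypertension, worst C-SSRS category, marked laboratory abnormalities and ECG/QTc abnormalities is not planned

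*SAP*

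**What the plan says.** Protocol Section 11.3 says safety data will be "presented separately for each phase as well as for the entire treatment period", meaning induction plus optimization/maintenance (OP/MA). The statistical section of the synopsis makes the same commitment. Neither limits it to particular kinds of safety data.

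SAP Section 6 first sets out safety data by phase on the Full analysis sets. It then adds that "adverse event and cognition data will be summarized for the entire treatment period combining the induction and optimization/maintenance phases", using the All Enrolled set. The detailed sections follow that split:

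- **SAP 6.3, vital signs.** Acute hypertension is summarized as "treatment-emergent acute hypertension (systolic BP ≥ 180 or diastolic BP ≥ 110) at any time during each treatment phase". Table 4 abnormalities are tabulated by phase, and for these "A listing of subjects meeting any of the following criteria during each treatment phase will also be provided".
- **SAP 6.2, laboratory.** Treatment-emergent markedly abnormal (TEMA) values, ALT above 3 times the upper limit and the Hy's Law combination are presented by phase, with a by-subject listing of markedly abnormal results for each phase.
- **SAP 6.4, ECG.** Abnormalities and QTc categories are based on values or maxima within a phase. A listing of subjects with abnormalities is planned.
- **SAP 6.6.1, C-SSRS.** Shifts from baseline "to the maximum category during each phase will be summarized". No subject listing is specified.

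SAP Section 1 says the document covers all planned analyses. Neither its amendment history nor its text gives a reason for the narrower scope.

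**The concern.** The primary objective (Protocol 2.1.1, SAP 1.1) names four areas for special attention: cognition, treatment-emergent adverse events, post-dose effects on heart rate, blood pressure, respiration and oxygen saturation, and suicidal ideation or behavior. The SAP keeps the whole-period view for the first two. It leaves it out for the measured data on the other two.

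A natural question for a long-term safety study is what share of treated subjects ever had the event while on study. Subject incidence does not add across phases. Some subjects pass through both phases and may have the event in one or both, some leave during induction, and others enter directly at OP/MA. A reader with only the two phase tables cannot answer the question for measured acute hypertension or for worst C-SSRS category.

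**Working it through.** **Scope.** The documents state no figure to reproduce, so the first check sets the planned outputs side by side.

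| Measure | By-phase table | Whole-period table | Subject listing |
|---|---|---|---|
| Adverse events, including special-interest categories | yes | yes | deaths, SAEs, discontinuations |
| Cognition | yes | yes | yes (SAP Attachment 2) |
| Table 4 vital-sign abnormalities | yes | no | yes, by phase |
| Acute hypertension | yes | no | only through the Table 4 listing |
| TEMA laboratory values | yes | no | yes, by phase |
| ALT/bilirubin criteria | yes | no | ALT and Hy's Law limits appear in Attachment 1 |
| ECG/QTc abnormalities | yes | no | yes |
| C-SSRS worst category | yes | no | none stated |

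**Why the phase tables are not enough.** Let a be the subjects with the event in induction, b those with it in OP/MA, and c those with it in both. Then

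whole-period count = a + b − c.

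The phase tables give a and b, never c. The denominators also differ. With n induction entrants, m of whom continue, and d direct entrants, the phase tables use n and m + d, while the whole-period denominator is n + d.

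**Illustration.** All counts here are assumed; the documents give no sample size or event rate.

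- n = 100, m = 90, d = 100; events in 5/100 (induction) and 19/190 (OP/MA). All OP/MA events could be in direct entrants (19 ≤ 100), so c can be 0. All induction events could recur (5 ≤ 90 and 5 ≤ 19), so c can be 5. The whole-period count is 19 to 24 of 200, or 9.5% to 12.0%.
- n = 300, m = 270, d = 100; events in 30/300 and 56/370. By the same reasoning c runs from 0 to 30. The whole-period count is 56 to 86 of 400, or 14.0% to 21.5%.

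Across nine such combinations (induction rates of 2%, 5% and 10%, paired with OP/MA rates of 5%, 10% and 15%, in three entry mixes), the range was 0.5 to 7.5 percentage points wide.

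For subjects who are in both phases, with one common denominator, the bounds are max(p1, p2) to p1 + p2; 5% and 10% would give 10% to 15%. No planned table uses that population. In the first mixed-entry example, 5% and 10% give a lower end of 9.5%, below that minimum.

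**How far the vital-sign listing helps.** Exclusion criterion 4 bars a predose first-day SBP above 140 mmHg (150 from age 65) or DBP above 90 mmHg. For an eligible subject whose baseline is that reading:

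- SBP ≥ 180 is a rise of at least 180 − 150 = 30; Table 4 asks for 20.
- DBP ≥ 110 is a rise of at least 110 − 90 = 20; Table 4 asks for 15, to ≥ 105.

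Eligibility deviations aside, every acute-hypertension case should therefore be in the Table 4 listing. It would also hold DBP-only cases of 105 to 109, which can be removed only if the listing shows values; the SAP does not say that it does.

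**The case against.** A reader might infer that the whole-period rates cannot be obtained at all. The documents do not support that. TEMA laboratory values, Table 4 vital signs and ECG abnormalities have subject listings, so subjects can be matched across phases by hand. Oxygen saturation below 93% is simply listed, with no phase restriction. Safety uses one Study Baseline by default (SAP 2.2), so the rates can be derived from the data.

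Nor is suicidality or blood pressure missing from the whole-period view altogether. Both are special-interest adverse event categories (SAP 6.1) and fall under the whole-period AE summaries. What is missing is the scheduled C-SSRS and the measured blood pressure. AE coding does not replace these, because it depends on the finding being reported as an event.

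Four further points deserve weight:

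- Protocol Section 11 calls itself a general description and leaves specifics to the SAP, and its laboratory paragraph speaks of time points in each phase. This softens the mismatch, but leaving out a promised summary is more than a detail.
- The study has no hypothesis and is descriptive, so no inference is affected.
- A pooled percentage mixes a 4-week phase with one of variable length. That is a reason to keep the phase tables, not to omit the pooled one.
- Protocol 6.1 requires some subjects with high post-dose pressures to discontinue dosing, so those induction events cannot recur in OP/MA. This limits c for acute hypertension but does not report it.

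**Conclusion.** The point holds as a minor but real gap between protocol and SAP. Whole-period subject incidence of the measures listed is not planned, and it cannot be worked out from the per-phase summary tables alone. C-SSRS is the clearest case, because it has neither a whole-period table nor a stated listing. Acute hypertension comes next, since it is recoverable only by re-screening a listing built on different criteria.

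The true size is unknown. The range of 0.5 to 7.5 percentage points rests entirely on assumed entry numbers and event rates. It shrinks to zero where no subject could have the event in both phases, or where subject-level data are used.

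**What to change.** Amend SAP Section 6 so that these subject-incidence summaries are also produced for the entire treatment period, on the All Enrolled set and against Study Baseline: Table 4 abnormalities, acute hypertension, TEMA values, ALT/bilirubin criteria, Table 5 ECG limits, Table 6 QTc criteria and worst C-SSRS category. Define a whole-period maximum for QTc and for the C-SSRS category, with the C-SSRS shift from Study Baseline. Keep the phase tables alongside.

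The analysis set and baseline already exist, so no new data are needed. For most incidence tables this means one more column. ECG and C-SSRS need a short re-derivation, because their post-baseline values or maxima are now defined within a phase. The pooled tables should carry a note that exposure time differs between subjects. If the sponsor prefers the narrower scope, the SAP should at least record and justify the departure from Protocol 11.3.
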